4.5.2.1 Programming the Pump

The Aortix Pump should initially be operated at a speed of 25 krpm for a minimum of two days. The pump may be stopped once congestion and hemodynamic targets have been achieved for that patient as assessed by the investigator. The pump should be left in place for a sufficient time to achieve the diuresis and hemodynamic goals for the patient. All adjustments are at the discretion of the investigator according to their clinical judgement. Once congestion and hemodynamic targets have been achieved, diuretic or other therapies may be down titrated or discontinued, at the physician's discretion, but the pump should be kept running at 25 krpm. **If a decision is made to reduce the Pump speed, vital signs, hemodynamic measurements and fluid ins and outs must be recorded before speed reduction in accordance with Appendix A.**

If congestion and hemodynamic targets have not been achieved after 2 days, the pump speed may be turned up in 1 krpm increments to see if running the pump at a higher speed will provide benefit to the patient.

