4.5.2.2 Monitoring Hemolysis and Adjusting Pump Speed

Careful monitoring for hemolysis should be coincident with adjusting the pump speed. Plasma free hemoglobin (pfH) (every 24 hours), LDH (every 12 hours) and urine hemoglobin^{xi} (every 12 hours) measurements should be taken while the pump is implanted to confirm there is no hemolysis. After every speed change (before the congestion target met/therapy deemed ineffective timepoint), pfH/LDH and urine hemoglobin measurements should be assessed before contemplating an additional speed change. As such, speed changes should only be made every 12 hours. Patients should be regularly monitored for signs of hemolysis (e.g. hemoglobinuria, cramping) as hemolysis may occur and not be recognized until the next pfH/LDH measurement. The maximum speed is 28k rpm.

Aortix Pump speed may be reduced to the last speed with no hemolysis if hemolysis or safety concerns arise.

^{xi} Only required if collected as part of routine standard of care urinalysis.

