4.5.3 Congestion Target Met/Therapy Deemed Ineffective Data Collection

Once the congestion target has been met or therapy has been deemed ineffective, before weaning begins, the following assessments should be made within 12 hours of beginning weaning:

- Cardiovascular exam (edema, pulmonary auscultation, weight)
- Vital Signs (HR, BP, RR)
- Dyspnea evaluation
- Fluid Ins and Outs since last reading
- Hemodynamics:
 - CVP
 - PA Systolic
 - PA Diastolic
 - PA Mean
 - PCWP
 - SvO2 as measured by the PA catheter
 - SaO2 as measured by pulse oximeter
- Echocardiogram
- Blood and urine labs per Appendix A
- Document any medication changes and adverse events

If the congestion target timepoint overlaps with a scheduled assessment (e.g, an every 24 hour hemodynamic measurement), the scheduled assessment value can be used and also entered on the congestion target met timepoint eCRF.

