4.5.4 Weaning the Pump Speed

Once the decision has been made to cease therapy, the pump speed may be adjusted down gradually (in increments of 2-5 krpm) while monitoring the patient's hemodynamics and urine output. The pump speed may be reduced to 18-20 krpm before it is retrieved. This process should ideally be conducted over a **minimum timeframe** of three hours with a minimum of two hours to reduce the speed to 18-20 krpm and a minimum of one hour of observation of the patient before removal. Only once in the cath lab and ready for retrieval should the Pump be turned OFF.

Figure 2 summarizes the pump programming steps.

[figure not shown]

Figure 2: Pump Programming

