5.3 Risk Mitigation

In addition, this protocol provides steps to mitigate risk to study patients. These include the following:

- Limited Study Size: A limited number of patients will receive the Aortix Pump in this study to determine performance and safety.
- Treatment Duration: The Aortix Pump will only remain implanted up to the point the investigator determines therapeutic goals have been reached. Alternatively, if the investigator determines Aortix Pump therapy is ineffective or unsafe, Aortix Pump may be retrieved at any time.
- Follow-up Assessments: Patients will be monitored closely for device performance, effectiveness, and adverse events.
- Investigator Selection: The investigators in this study are selected based on their experience in performing large bore cardiovascular interventional procedures and experience treating patients with ADHF with worsening renal function.
- Site Selection: Study sites will have sufficient expertise and resources to manage adverse events and provide appropriate alternative therapies if needed.
- Investigator Training: Investigator(s) will be trained in proper device operation prior to study start. Training will include didactic and hands-on training with the Aortix System.
- Subject Screening: The study protocol includes appropriate precautions in patient selection. For example, patients with known anatomic incompatibilities, significant co-morbidities or uncontrolled cardiovascular or other disease will be excluded.
- Adverse Event Monitoring: Timely detection, treatment, and reporting of all adverse events.
- Adverse Event Monitoring: Enrollment pause based on occurrence of procedural related death or serious procedural related adverse events (see Section 6).
- Independent Safety Monitoring. Use of an external clinical events committee for safety monitoring with timely adjudication of adverse events.

6. Adverse Events

Adverse event definitions used in the study are based on ISO 14155:2011 (Clinical Investigation of Medical Devices for Human Subjects – Good Clinical Practice) as defined below. Specific definitions of key Adverse Events are listed in **Appendix C: Key Adverse Event Definitions**. The Clinical Event Committee may elect to further modify or add to the definitions.

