Appendix C: Key Adverse Event Definitions

Minor Hemolysis	
A plasma free Hemoglobin (pfH) greater than 20 mg/dL or a serum lactate dehydrogenase (LDH) greater than two and one half times (2.5x) the upper limits of the normal range at the implanting center occurring after the first 72 hours post-implant in the absence of clinical symptoms or findings of hemolysis or abnormal pump function (see Major Hemolysis for a list of symptoms and findings) and thought not attributable to laboratory error.

Major Hemolysis	
A pfH value greater than 20 mg/dl or a serum LDH greater than two and one half times (2.5x) the upper limits of the normal range at the implanting center occurring after the first 72 hours post-implant and associated with clinical symptoms or findings of hemolysis or abnormal pump function. Major Hemolysis requires the presence of at least one of the following conditions:
 
 • Hemoglobinuria (“tea-colored urine”) • Anemia (decrease in hematocrit or hemoglobin level that is out of proportion to levels explainable by chronic illness or usual post-VAD state) • Hyperbilirubinemia (total bilirubin above 2 mg/dL, with predominately indirect component) • Pump malfunction and/or abnormal pump parameters
Bleeding: Life Threatening or Disabling	
 • Fatal bleeding (BARC type 5) OR • Bleeding in a critical organ, such as intracranial, intraspinal, intraocular, or pericardial necessitating pericardiocentesis, or intramuscular with compartment syndrome (BARC type 3b and 3c) OR • Bleeding causing hypovolemic shock or severe hypotension requiring vasopressors or surgery (BARC type 3b) OR • Overt source of bleeding with drop in hemoglobin ≥ 5 g/dL or whole blood or packed red blood cells (RBCs) transfusion ≥ 4 units* (BARC type 3b)
Bleeding: Major Bleeding (BARC type 3a)	
 • Overt bleeding accompanied by hemoglobin drop of 3 to < 5 g/dL (1.86 to 3.1 mmol/L SI Units) (provided hemoglobin drop is related to bleed) • Any transfusion with overt bleeding

Bleeding: Minor bleeding (BARC type 2)	
 Any bleeding worthy of clinical mention (e.g., access site hematoma) that does not qualify as life-threatening, disabling, or major

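### On their natural reading, both hemolysis labels start only after 72 hours post-implant although support may end sooner, and the SAP text defines no rate for the listed hemolysis outcome

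*Protocol*

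**What the plan says.** **Definitions.** Protocol Appendix C sets the same laboratory thresholds for both labels: pfH above 20 mg/dL, or LDH above 2.5 times the center's upper limit. For Minor Hemolysis the text continues from the LDH limit as "the normal range at the implanting center occurring after the first 72 hours post-implant in the absence of clinical symptoms". For Major Hemolysis the finding must be one "occurring after the first 72 hours post-implant and associated with clinical symptoms or findings of hemolysis or abnormal pump function".

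**Duration of support.** Protocol Section 4.5.2.1 states: "The Aortix Pump should initially be operated at a speed of 25 krpm for a minimum of two days". It then lets the pump be stopped once the patient's targets are reached. Section 5.3 adds that "if the investigator determines Aortix Pump therapy is ineffective or unsafe, Aortix Pump may be retrieved at any time". Section 4.5.4 describes an ideal wean with "a minimum of two hours to reduce the speed to 18-20 krpm and a minimum of one hour of observation". Section 4.5 says the pump has been tested for 7 days of use.

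**Sampling.** Protocol Section 4.5.2.2 schedules pfH every 24 hours, and LDH and urine hemoglobin every 12 hours (urine hemoglobin only where it is part of routine urinalysis). It says these "measurements should be taken while the pump is implanted to confirm there is no hemolysis". Appendix A adds draws at Congestion Target Met, in the cath lab before retrieval (pfH and LDH), and after retrieval.

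**Planned analysis.** Protocol Section 3.3.4 and SAP Section 5.4 list rates of hemolysis by LDH, pfH and urine hemoglobin. SAP Section 7.9.2 plans a summary of these three at Day of Implant, Congestion Target Met, Post 72Hrs or Discharge, and Follow-Up, with listings and individual plots.

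**The concern.** The labels seem not to fit the period of exposure. The trial measures hemolysis from the start of support, but the two named event categories apply only from the fourth day. A patient whose pump comes out at two days, or earlier because of a safety concern, cannot have any on-pump result labelled.

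No threshold-based laboratory rate is stated in the SAP text to fill the gap. A count of labelled events would then be the most visible hemolysis figure, and it would be silent on early support.

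This matters because the protocol contrasts the device with existing pumps on hemolysis (Section 1.1), suggests the risk may be lower with this device (Section 5.2), and intends the pilot data to inform later studies (Section 7).

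**Working it through.** The plan gives no hemolysis rate, so there is no figure to reproduce. The check counts which scheduled draws can meet the definition.

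**Step 1: routine on-pump draws.** LDH is drawn at 12, 24, ..., H hours and pfH at 24, 48, ..., H hours, where H is the duration of support. A draw can qualify only if it falls after 72 hours.

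| Support H | LDH able to qualify | pfH able to qualify |
|---|---|---|
| 48 h | 0 of 4 | 0 of 2 |
| 72 h | 0 of 6 | 0 of 3 |
| 96 h | 2 of 8 | 1 of 4 |
| 120 h | 4 of 10 | 2 of 5 |
| 168 h | 8 of 14 | 4 of 7 |

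Even at the longest tested duration, 72/168 = 43% of support lies inside the excluded window. With support beyond 72 hours, a nominal 72-hour draw could fall just past the limit because of the visit windows.

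**Step 2: extra on-pump draws.** If the Congestion Target Met and cath-lab draws are separate and both fall after 72 hours, each count gains two in numerator and denominator. At 96 h this gives 4 of 10 LDH and 3 of 6 pfH; at 168 h, 10 of 16 and 6 of 9. With support of 72 hours or less they add nothing that can qualify.

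**Step 3: after an early retrieval.** Two days plus the ideal three-hour wean is 48 + 3 = 51 h. The first scheduled post-retrieval draw is due 24 h later, with a 2 h window: 51 + 22 = 73 h to 51 + 26 = 77 h post-implant. It can qualify, but it is already 22 to 26 h off the pump.

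**Step 4: how many patients.** The documents do not give the share retrieved by 72 hours. If it were 10%, 50% or 90% (assumptions), then 30 × 0.9 = 27, 30 × 0.5 = 15 or 30 × 0.1 = 3 of 30 implanted patients could have a qualifying on-pump value.

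**Step 5: the SAP's four timepoints against Protocol Appendix A.**
- Day of Implant is before the pump is placed.
- Congestion Target Met is on the pump, since "the following assessments should be made within 12 hours of beginning weaning" and before weaning starts.
- Post 72Hrs or Discharge is off the pump.
- Follow-Up has no scheduled pfH, LDH or urine hemoglobin.

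Only one of the four named timepoints is on pump. SAP Section 3.1, however, says data are shown at every scheduled timepoint where applicable. The two sections need to be reconciled.

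**The case against.** The strongest reply is that early hemolysis is not lost, and most of that stands.
- The general adverse event definition (Protocol Section 6.2) includes abnormal laboratory findings, and Section 6 says to report when unsure. Early events can therefore enter the SAE percentage, the device-related percentage and the adverse event tables (SAP Sections 7.8.1, 7.8.2 and 7.9.1).
- Values are listed and plotted by patient, which suits a pilot that reviews each patient individually.
- Hemolysis monitoring and the related pump-speed provisions carry no 72-hour limit.
- The opening of Protocol Section 6 says "The Clinical Event Committee may elect to further modify or add to the definitions".
- A 72-hour limit may be meant to screen out transient procedural rises, although neither document says so.

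Two things remain. Section 6 leaves isolated laboratory rises to investigator discretion, and Minor Hemolysis is by definition without clinical findings. The committee's power is a permission, and no change to the limit is specified.

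The wording is also open to another reading: grammatically, the 72-hour phrase could attach to LDH alone. Early pfH values would then count (2 of 2 routine draws at 48 h) and the gap would narrow to LDH. This should be clarified.

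A reader might draw stronger conclusions that the documents do not support:
- *A rise must persist off the pump to be labelled after short support.* Appendix C is not limited to scheduled draws, and a new rise after retrieval would also qualify.
- *Routine draws enter no summary, or the tables hold no threshold.* SAP Section 3.1 may bring the routine draws in, and only table titles are shown.
- *The hemolysis summary will contain no on-pump value.* SAP Section 7.14 says Congestion Target Met is not collected in the latest CRF, but only in relation to urine output. That is a separate question.
- *The first-in-human finding of no hemolysis follows from this clause.* That was a separate study, and the documents do not say which definition it used.
- *Zero labelled events in 30 would be used to bound the risk.* No such inference is planned.

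**Conclusion.** The concern holds in two parts. First, on the natural reading of Appendix C, no on-pump value can be labelled as hemolysis in a patient supported for 72 hours or less, and with longer support only the later draws can. Second, hemolysis rates are a listed outcome for which SAP Section 7.9.2 states no threshold, numerator or denominator.

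The conclusion rests on the 72-hour phrase covering both pfH and LDH, and on the nominal draw schedule. A labelled count could understate on-pump hemolysis. By how much is unknown, because neither the distribution of support duration nor the frequency of early rises is given. A reader might infer that the primary safety endpoints are biased; the documents do not show that, because a serious early event can be counted whatever its label. Severity is minor to moderate, with moderate confidence.

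**What to change.** 1. In SAP Section 7.9.2 and Tables 14.3.4.3.1 and 14.3.4.3.2, add the number and percentage of As-Treated patients (PSC patients in the second table) with any on-pump pfH above 20 mg/dL or LDH above 2.5 times the site's upper limit.
   - Use all on-pump draws: routine, speed-change, Congestion Target Met and cath-lab.
   - Split at or before 72 hours versus after 72 hours. The denominator of the later row is the patients still on the pump past 72 hours.
   - Show patients already above threshold at the Day of Implant draw on a separate row.
   - State how the timepoints named in Section 7.9.2 relate to the general rule in Section 3.1.

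2. For event labelling only, reconcile the 72-hour clause with the permitted support duration, and state whether it covers pfH as well as LDH. This can be done by protocol amendment or through the Clinical Event Committee.

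**Cost.** Item 1 is a few derived rows using scheduled draws and existing thresholds, plus each site's LDH upper limit. An amendment under item 2 needs EC/IRB approval (Protocol Section 8.3). On the committee route, the charter is ratified before any event review (Section 6.3), and events already adjudicated may need re-review. Some transient procedural rises will be counted and the figure may look less favorable; the 72-hour split and the Day of Implant row keep these visible.

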CRF	Case Report Form

Abbreviation or special term	Explanation
CRRT	Continuous Renal Replacement Therapy
CRS	Cardiorenal Syndrome
CRT	Cardiac Resynchronization Therapy
CVP	Central Venous Pressure
ECMO	Extracorporeal Membrane Oxygenation
eCRF	Electronic Case Report Form
EDC	Electronic Data Capture
EF	Ejection Fraction
eGFR	Estimated Glomerular Filtration Rate
EQ5D	the EuroQol-5D, an instrument developed in Europe and widely used, which evaluates the generic quality of life
GCP	Good Clinical Practices
HF	Heart Failure
HFpEF	Heart Failure with a Preserved Ejection Fraction
HFrfEF	Heart Failure with reduced Ejection Fraction
HIPAA	Health Insurance Portability and Accountability Act
HR	Heart Rate
IA	Interim Analysis
ICF	Informed Consent Form
ICU	Intensive Care Unit
KCCQ	Kansas City Cardiomyopathy Questionnaire
LDH	Lactate Dehydrogenase
LVAD	Left Ventricular Assist Device
LVEDV	Left Ventricular End-Diastolic Volume
LVEF	Left Ventricular Ejection Fraction
LVESD	Left Ventricular End-Systolic Dimension
LVESV	Left Ventricular End-Systolic Volume
MAP	Mean Arterial Pressure

Abbreviation or special term	Explanation
NT-pro-BNP	N-terminal pro B-type Natriuretic Peptide
NYHA	New York Heart Association
PA	Pulmonary Artery
PAC	Pulmonary Artery Catheter
PAP	Pulmonary Artery Pressure
PCWP	Pulmonary Capillary Wedge Pressure
PDV	Protocol Deviation
pfH	Plasma Free Hb
QoL	Quality of Life
RR	Respiratory Rate
SADE	Serious Adverse Device Effect
SAE	Serious Adverse Event
SAP	Statistical Analysis Plan
SD	Standard Deviation
SPRAE	Serious Procedure Related Adverse Events
TEAE	Treatment-Emergent Adverse Event
TFLs	Tables, Listings, and Figures
USADE	Unanticipated Serious Adverse Device Effect
WRF	Worsening Renal Function

1 INTRODUCTION

This statistical analysis plan (SAP) describes the statistical methods and data handling methods to be followed during final reporting and any interim analyses of data collected for the study Protocol PVP017.

This SAP should be read in conjunction with the study protocol and case report form (CRF). This version of the plan has been developed using the protocol Rev G, CRF dated Jan 12, 2022, and Medication Memo dated Mar 9, 2022.

2 STUDY DETAILS

2.1 Study Objectives

The **objectives of the study** are:

- Safety:
 - Observe the nature, severity, and frequency of adverse events associated with the delivery, use, and retrieval of the Aortix Pump.
- Performance:
 - Successfully deliver the Aortix Pump to the descending thoracic aorta using the Aortix Delivery System;
 - Aortix Pump shall function as programmed for the duration of therapy;
 - Manage the Aortix Pump Power Lead and access site over the course of therapy without significant complications;
 - Successfully retrieve and remove the Aortix Pump using the Aortix Retrieval System.
- Effectiveness:
 - Evaluate hemodynamic decongestion (CVP, PCWP) during Aortix therapy;
 - Evaluate the effect of the Aortix therapy on kidney function;
 - Evaluate the impact of the Aortix Pump on clinical biomarkers of congestion.

2.2 Study Design

The study is a prospective, multi-center, non-randomized feasibility study to evaluate the safety and performance of the Aortix System in patients hospitalized with acute decompensated heart failure (ADHF) irrespective of ejection fraction and worsening renal function refractory to medical management with persistent congestion.

2.3 Determination of Sample Size

The sample size of up to thirty (30) implanted patients is based upon industry standards for early stage studies of medical devices; the sample size was not statistically derived.

The study will provide data to be used for demonstrating initial device safety and effectiveness in this patient population, as well as providing input for design of future clinical studies of the device. It is estimated that approximately 50% of patients enrolled may not receive the pump due to anatomical requirements or right heart PA catheterization requirements not being met or inability to implant the pump. Therefore, we plan to enroll up to 60 patients to yield 30 implanted patients.

3 DATA ANALYSIS CONSIDERATION

3.1 General Considerations

The statistical analyses will be performed using SAS Version 9.4 (or higher). All tables, figures and listings will be produced in landscape format.

Data will be presented at each scheduled timepoint (nominal time), where applicable.

The total number of patients in the study group (N) under the stated set of patients will be displayed in the header of summary tables.

All study data will be included in the study data listings. If not stated otherwise listings will be displayed by patient in chronological order.

3.2 General guideline for descriptive summaries

For continuous variables, mean, median, standard deviation, minimum and maximum will be presented for each subgroup and category.

For categorical variables, count and % of patients/counts in each subgroup and/or category will be presented. Percentages will be based on the number of patients with non-missing values, if not specified otherwise.

4 DEFINITION

Baseline, if not specified differently, will be defined as the last non-missing measurement collected during Pre-Implant Period (Baseline Monitoring). For parameters that are not collected during the corresponding time period, the baseline will be defined as the last non-missing measurement prior to Aortix Pump implantation procedure.

TEAEs will be defined as AEs not present prior to the start of study procedures, or AEs present before study treatment that worsened after the implantation procedure. If a partially missing date or time of onset allows the possibility that an AE may be a TEAE it will be assumed that it is a TEAE.

